3.2 Neonatal Variables

The following characteristics will be collected for the neonate in addition to the neonatal echo (for details please see annotated CRF):

- Gestational age at birth (weeks and days)
- Gender
- Mode of delivery (vaginal, caesarean)
- Apgar score (at 1 min and 5 min)

STATISTISKA KONSULTGRUPPEN	Statistical Analysis Plan
Protocol:	Protocol No:
Effect of fetal aortic valvuloplasty on outcomes	

Version:	
1.0	Page 16 of 26

- Birth weight (g)
- Birth weight standard deviation score (SDS)
- Birth height (cm)
- Birth height SDS
- Body surface area (BSA) (m²)
- Head circumference (cm)
- Head circumference SDS
- Intention to treat
- Emergency procedures before 24 hrs of age
- Prostaglandin treatment
- Inotropic drugs
- Diagnostic details of the left heart before postnatal intervention
- Other clinical cardiac diagnoses before intervention
- Initial surgical pathway
- Clinical cardiac diagnoses at neonatal discharge
- Non-cardiac diagnoses at neonatal discharge

3.3 Follow-up at Two Years Variables

The following variables will be collected at two years follow-up.

- Age at follow-up (months)
- Weight (kg)
- Weight SDS
- Height (cm)
- Height SDS
- Type of circulation (univentricular or biventricular)
- Pulmonary hypertension if biventricular

STATISTISKA KONSULTGRUPPEN	Statisti	cal Analysis Plan
Protocol: Effect of fetal aortic valvuloplasty on outcomes	Protocol No	D:
	Version: 1.0	Page 17 of 26

- Detailed cardiac diagnosis
- Non-cardiac diagnoses
- Neurological sequelae
- List of all cardiac surgical and catheter procedures performed

3.4 Efficacy Variables

3.4.1 Primary Efficacy Variable

The primary efficacy variable is transplantation-free survival until 2 years postnatal age, having a biventricular circulation without pulmonary hypertension at that time. Diagnosis of pulmonary hypertension will be based on catheter/echo/clinical data and graded as mild, moderate or severe. This means that death, transplantation and biventricular circulation with pulmonary hypertension or no biventricular circulation will be part of this composite endpoint coded as yes/no. This variable cannot be analysed as time to event variable due to the fact that biventricular circulation and pulmonary hypertension are evaluated at 2 years of age. Early discontinuations for other reasons than death, without transplantation and with biventricular circulation without pulmonary hypertension at the time of early discontinuation will be counted in no event group.

The primary variable will be analysed on FAS_{ENR} (main analysis), FAS_{BIRTH}, PP_{ENR} and PP_{BIRTH}, overall for FAV 1+2 vs no-FAV 1+2 (main analysis), and descriptively FAV 1 vs no-FAV 1 and FAV 1 vs no-FAV 1+2.

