#### **Primary objective**

To evaluate if fetal valvuloplasty in aortic stenosis improves outcomes up to 2 years after birth compared with no fetal valvuloplasty, measured with transplantation-free survival from fetal diagnosis to 2 years postnatal age with a biventricular circulation without pulmonary hypertension at that time.

Absence of pulmonary hypertension is defined as a TR max velocity  $\leq 2.8$  m/s with no other echocardiographic signs of pulmonary hypertension and/or catheter data showing a mean pulmonary arterial pressure <25 mmHg (11,12).

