## Electronic case report forms (eCRF)

There are 14 eCRF's:

1. eCRF Inclusion criteria

All inclusion and no exclusion criteria need to be satisfied for a case to be included.

2. eCRF Inclusion

Include case if inclusin/exclusion criteria satisfied.

3. eCRF Counselling on fetal aortic valvuloplasty

If councelling was performed and, if so, what the decision was.

4. eCRF Baseline fetal echo 23+0 - 31+6

The baseline fetal echo is performed between 23+0 and 31+6 weeks. If an intervention is performed, the last exam before the intervention should be used as baseline fetal echo.

5. eCRF Additional baseline fetal echo 23+0 - 31+6

In case there is a late descision to perform an intervention, after a baseline fetal echo has already been submitted, there is an option to add an additional baseline fetal echo in the system.

6. eCRF Fetal interventions

A new eCRF Fetal interventions should be added for each intervention performed.

7. eCRF Follow-up fetal echo 33+0 - 34+6

The follow-up fetal echo is performed between 33+0 and 34+6 weeks.

8. eCRF Neonatal - Birth

Gestational age and size at birth, mode of delivery and pharmacological support.

9. eCRF Neonatal - Echo

First full study after birth, and before the first postnatal intervention, surgery or cath (except emergency atrial septostomy)

10. eCRF Neonatal - Cardiac clinical diagnosis

Cardiac diagnoses before the first intervention, surgery or cath (except emergency atrial septostomy)

11. eCRF Neonatal - Neonatal discharge

Type of circulation and clinical diagnoses at discharge.

12. eCRF Follow-up at 2 years of age

Type of circulation, clinical diagnoses, pulmonary hypertension, neurological sequealae, somatic growth.

13. eCRF Postnatal procedures

All cardiac surgical and catheter interventional procedures from birth to 2 years follow-up

14. eCRF Subject termination

Reason for subject termination including completion at 2 years of age.

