4.6 Efficacy Analyses

4.6.1 Primary Efficacy Analysis

Primary efficacy analysis, test between FAV vs no-FAV regarding transplantation-free survival from fetal diagnosis to 2 years postnatal age, having a biventricular circulation without pulmonary hypertension at that time, will be performed using logistic regression adjusted for confounders identified according to the section General Methodology above. OR with 95% CI will be presented. The primary analysis will be performed on FAS_{ENR} population and will compare FAV 1+2 versus no-FAV 1+2. This analysis will be included in the evaluation of the confirmatory tests. Complementary analyses will be performed on FAS_{BIRTH}, PP_{ENR}, PP_{BIRTH} populations, and on all populations comparing FAV 1 with no–FAV 1 and FAV 1 vs no-FAV 1+2.

Sensitivity analyses will be performed using Fisher's exact test comparing the FAV group with the matched no-FAV group obtained applying propensity score matching according to the description in General Methodology above, both on FAS and PP populations.

Vertical bar charts will be presented for graphical purpose.

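### SAP 3.4.1 scores early discontinuers who were biventricular without pulmonary hypertension as 2-year successes; the bias depends on loss in each arm, and no analysis tests it

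*SAP*

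**What the plan says.** SAP 3.4.1 defines the primary variable as "transplantation-free survival until 2 years postnatal age, having a biventricular circulation without pulmonary hypertension at that time". It lists the failures: "death, transplantation and biventricular circulation with pulmonary hypertension or no biventricular circulation will be part of this composite endpoint coded as yes/no". No event therefore means success. The paragraph rules out a time-to-event analysis on the ground that "biventricular circulation and pulmonary hypertension are evaluated at 2 years of age".

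It then deals with children who discontinue for reasons other than death, without a transplant. Those "with biventricular circulation without pulmonary hypertension at the time of early discontinuation will be counted in no event group". Children who are univentricular or have PH when they leave, and live fetuses withdrawn before birth, are not mentioned.

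The coded variable feeds the confirmatory analysis in SAP 4.6.1, which "will be performed using logistic regression adjusted for confounders identified according to the section General Methodology above" on the enrolled full analysis set and is the first test in the fixed sequence of SAP 4.1. The only sensitivity analysis described for the primary variable is propensity-score matching (SAP 4.1 and 4.6.1). The sample size sections of both documents make no allowance for missing 2-year outcomes.

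PH is described in two ways. SAP 3.4.1 says: "Diagnosis of pulmonary hypertension will be based on catheter/echo/clinical data and graded as mild, moderate or severe". The protocol's Primary objective and the SAP's List of definitions use a threshold instead: a tricuspid regurgitation velocity limit "with no other echocardiographic signs of pulmonary hypertension and/or catheter data showing a mean pulmonary arterial pressure" below 25 mmHg.

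**The concern.** The paragraph fixes the assessment at 2 years and then accepts an earlier assessment in its place. This is last status carried forward on the confirmatory endpoint. It treats an unobserved outcome as known, so it can distort the estimate and also understates its uncertainty.

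The rule need not affect the arms equally. The hypothesis is that fetal valvuloplasty leads to more biventricular survival. If it raised only the early biventricular share and those circulations later failed, carrying the early status forward would credit it with a 2-year benefit. The matched analysis offers no protection, because it uses the same coded outcome.

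A second, smaller matter is that SAP 3.4.1 does not refer to the threshold definition of PH, and the wording of PH decides who is a success.

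**Working it through.** **The plan's own figure.** Full enumeration of the two-sided Fisher test at alpha 0.05 with 100 FAV and 50 no-FAV, 60% against 30%, gives 92.7% power; the plan states 91.8%. The figures are close and the power statement is not in dispute. It assumes that every 2-year outcome is known. With 30% in both arms the same test rejects in 4.0% of trials, which is the reference below.

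**Formula.** For each arm let

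- e = share biventricular without PH at last contact before 2 years,
- f = share of those who fail by 2 years,
- d = share lost before 2 years, taken as unrelated to later failure.

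True success is e(1 − f). Under the SAP rule scored success is e(1 − f) + d·e·f, so each arm gains d·e·f. This assumes that children who are not biventricular without PH at last contact are scored as failures and do fail.

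**Inputs.** From the documents: 100 and 50 subjects, alpha 0.05 two-sided, 30% success in no-FAV. Assumed, because the documents give no values: true success of 30% in both arms, e of 55–70% in FAV and 40–45% in no-FAV, and the loss rates. These inputs fix f = 1 − 0.30/e, which is 45–57% in FAV (1 − 0.30/0.55 to 1 − 0.30/0.70) and 25–33% in no-FAV (1 − 0.30/0.40 to 1 − 0.30/0.45). The scenario therefore builds in more late failure in FAV.

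**Worked case.** 20% loss in both arms, e = 70% and 40%:

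- FAV gain = 0.20 × (0.70 − 0.30) = 8 points, scored 38%.
- No-FAV gain = 0.20 × (0.40 − 0.30) = 2 points, scored 32%.
- Spurious difference = 6 points; rejection 9.6%.

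The step uses d·e·f = d(e − 0.30), since e(1 − f) = 0.30. With equal d the difference reduces to d × (e in FAV − e in no-FAV).

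**All pairings of the assumed early shares:**

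| Loss, FAV / no-FAV | Spurious difference (points) | Fisher rejection |
|---|---|---|
| none | 0 | 4.0% |
| 10% / 10% | +1.0 to +3.0 | 4.2–5.4% |
| 20% / 20% | +2.0 to +6.0 | 4.7–9.6% |
| 20% / 10% | +3.5 to +7.0 | 5.9–11.7% |
| 10% / 20% | −0.5 to +2.0 | 4.1–4.7% |

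**Under the design effect.** With true success of 60% against 30%, the same f of 10–30% in both arms and 10% loss, the scored difference is 30.3 to 31.3 points. The bias is +0.3 to +1.3 points.

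The rejection rates are for the unadjusted Fisher test. The primary test is adjusted logistic regression, so they indicate scale only.

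**The case against.** Several points on the other side are sound.

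- **Direction.** A reader might infer that the rule always favours FAV. It does not: the last row of the table reaches −0.5 points. Nothing in the documents suggests that FAV loses more children than no-FAV.
- **Late failure.** The null scenario needs much more late failure in FAV. If late failure and loss are equal in the two arms and there is no true effect, early status is also equal and the bias is zero.
- **One-sidedness.** A reader might infer that missing outcomes are imputed only as successes. The text names only the success case, but a child last seen univentricular or with PH would presumably be scored as an event under the composite. The calculation above assumes so.
- **Unmeasured PH.** PH is a named item only at 2 years ("Type of circulation, clinical diagnoses, pulmonary hypertension, neurological sequealae, somatic growth"), so one might infer that PH at discontinuation cannot be known. That goes too far. The neonatal echo, the diagnoses at discharge and the postnatal procedures are also recorded, and the annotated eCRF is not among the documents.
- **Grade of PH.** SAP 3.4.1 already makes a biventricular circulation with PH an event, without a limit on grade. The documents also give no basis for estimating how often echo and catheter data disagree.
- **Safeguards.** The follow-up figure shows a window of 24 to 36 months, and SAP 4.2 tabulates withdrawals by reason and group, so heavy use of the rule could be seen.

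These points limit the direction and size of the bias. They do not justify the rule. A withdrawal table shows how many children left, not what the result would have been under another assumption.

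**Conclusion.** The concern stands in conditional form. SAP 3.4.1 counts an unobserved 2-year outcome as a success in the confirmatory analysis, and no planned analysis varies that assumption. With similar loss in the two arms and equal true 2-year success, the rule favours the arm with more early biventricular circulations; with higher loss in no-FAV it can be neutral or reversed.

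Under the assumed inputs the bias is small at 10% loss per arm, where the rejection rate stays near the nominal 5%. It can become material at 20% loss, where rejection reaches 9.6% at the upper end. All these figures rest on assumed loss, early status and late failure. The documents do not support a claim that the trial will be biased towards benefit; they support a claim that it could be and that the plan would not show it. The point should be fixed, but it does not undermine the design.

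The PH wording is secondary. The description by data source and grade, which admits clinical data, and the threshold definition are not tied together, and the and/or in the latter does not settle discordant echo and catheter data.

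**What to change.** Before outcomes are examined by arm, replace the sentence in SAP 3.4.1 as follows.

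1. The 2-year status of a child who discontinues early is missing, unless death, transplantation or an established univentricular circulation has been observed. State that this includes live fetuses withdrawn before birth.
2. The primary analysis uses multiple imputation by arm, from the baseline covariates, circulation at neonatal discharge where available, and last known status.
3. Sensitivity analyses score all such cases as failures and add a tipping-point analysis that varies the assumed success of missing cases separately in each arm.
4. Missing 2-year status is reported by arm.

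Separately, the sponsor should reconcile the PH wording in SAP 3.4.1 with the threshold definition in the protocol's Primary objective and the SAP's List of definitions, and state how that definition treats discordant echo and catheter data. Which reading applies is for the sponsor to settle.

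The cost is SAP wording, a little programming and a slightly wider confidence interval. The all-failure analysis has lower power by construction: at 60% against 30%, Fisher power is 87.9% with 10% loss and 81.0% with 20% loss, against 92.7% with none. It therefore belongs among the sensitivity analyses. If loss proves negligible, the change alters almost nothing.

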3.4.2 Secondary Efficacy Variables

Secondary efficacy variables in this study are as following:

- Transplantation-free survival from fetal diagnosis to 2 years of age (analysed as time to event on FAS_{ENR} (main analysis), FAS_{BIRTH} (followed from birth), PP_{ENR} and PP_{BIRTH} (followed from birth), overall for FAV 1+2 vs no-FAV 1+2 (main analysis), and descriptively FAV 1 vs no-FAV 1 and FAV 1 vs no-FAV 1+2).
- Survival from fetal diagnosis to live birth (analysed as time to event on FAS_{ENR} (main analysis) and PP_{ENR}, overall for FAV 1+2 vs no-FAV 1+2 (main analysis), and descriptively FAV 1 vs no-FAV 1 and FAV 1 vs no-FAV 1+2).

Protocol

Statistical Analysis Plan

Effect of fetal aortic valvuloplasty on outcomes

- Proportion of included patients who have a biventricular circulation at neonatal hospital discharge (analysed on FAS_{ENR} (main analysis), FAS_{BIRTH}, PP_{ENR} and PP_{BIRTH}, overall for FAV 1+2 vs no-FAV 1+2 (main analysis), and descriptively FAV 1 vs no-FAV 1 and FAV 1 vs no-FAV 1+2).
- Proportion of included patients who have a biventricular circulation at 2 years of age (analysed on FAS_{ENR} (main analysis), FAS_{BIRTH}, PP_{ENR} and PP_{BIRTH}, overall for FAV 1+2 vs no-FAV 1+2 (main analysis), and descriptively FAV 1 vs no-FAV 1 and FAV 1 vs no-FAV 1+2).
- Number of postnatal catheter and/or surgical procedures before 2 years of age (analysed on FAS_{BIRTH} (main analysis) and PP_{BIRTH}, overall for FAV 1+2 vs no-FAV 1+2 (main analysis), and descriptively FAV 1 vs no-FAV 1 and FAV 1 vs no-FAV 1+2).

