1.2 Study Design

The study is an international multicenter prospective observational cohort study with a comparison cohort. Included are fetuses with a diagnosis of aortic stenosis who satisfy inclusion/exclusion criteria between 23+0 and 31+6 weeks of gestation. The decision whether a fetal balloon dilatation shall be attempted is not part of the study protocol. The number of examinations of mother/fetus/infant in this study is not different from the number of examinations that will be recommended for someone choosing not to be part of this study. The participation in the study is not affecting the treatment mothers and fetuses are receiving during pregnancy, nor how the infant is examined and treated after birth. The aim of the study is to, in a prospective and organized way, collect and evaluate multi-center data in order to reduce the risk for selection bias, missing data and inter-variability between participating centers.

Cases will be recruited from centers offering fetal aortic valvuloplasty and and from centers not offering this treatment. All intervention cases will be recruited from high volume

Protocol

Statistical Analysis Plan

Effect of fetal aortic valvuloplasty on outcomes

1.0

intervention centres which have performed at least 20 fetal cardiac interventions during the last five years before including the first case in the study. Fetal and postnatal echocardiographic examinations will be reviewed and remeasured by a core laboratory to confirm eligibility for inclusion, and identify potential measurement errors.

Data from two fetal echoes and one postnatal will be collected and each contains a comprehensive set of two-dimensional and Doppler measurements which will enable analysis of cardiac growth and development during pregnancy. Analysis of change of dimensions of the left heart structures and selected hemodynamic variables from the point of study inclusion until just before the first postnatal catheter or surgical procedure provides an opportunity to make a comparison between the groups that is unbiased with respect to centerspecific postnatal treatment policies. Three echocardiographic examinations and a 2-year follow-up regarding patient outcome will be performed as per Figures 1-3 below.

Figure 1. Study Overview – Fetal Protocol

STATISTISKA KONSULTGRUPPEN	Statistic	cal Analysis Plan
Effect of fetal aortic valvuloplasty on outcomes	Protocol No:	
	Version: 1.0	Page 8 of 26

Figure 2. Study Overview – Neonatal Protocol

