3 STUDY VARIABLES

3.1 Fetal and Pregnancy Variables

The following characteristics regarding the pregnancy and the fetus will be collected at inclusion and baseline fetal echo:

- Gestational age at primary diagnosis (weeks and days) (potential confounder)
- Year of diagnosis (potential confounder)
- Primary diagnostic hospital, city and country

Statistical Analysis Plan

Protocol No:

Effect of fetal aortic valvuloplasty on outcomes

- Average yearly case volume of center performing fetal intervention (potential confounder)
- Gestational age at baseline fetal echo (weeks and days) (potential confounder)
- Hospital, city and country where each echo was performed
- Maternal age
- Parity

Protocol

- Multiple pregnancy (potential confounder)
- Mother's body mass index (BMI) (potential confounder)
- Maternal comorbidities
- Maternal contraindications to fetal intervention
- Echo data (baseline fetal echo). Only those considered as potential confounders listed here (for a full set of variables for all three echoes, 2 fetal and 1 neonatal, please see the annotated eCRF):
 - Left ventricular end-diastolic diameter (mm and z-score) (potential confounder)
 - Left ventricular inlet length in diastole (mm and z-score) (potential confounder)
 - Mitral valve diameter, 4 ch view in end diastole (potential confounder)
 - Aortic valve annulus diameter (mm) (potential confounder)
 - Mitral valve inflow pattern (Biphasic; Fused; Monophasic; No inflow) (potential confounder)
 - LV:RV inlet length ratio (potential confounder)

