Effect of fetal aortic valvuloplasty on outcomes

Protocol No:

screening policies) and gestational age at inclusion. Most probably they are highly correlated and in that case the more influential of the two will be used.

Variables listed under 3.1 as potential confounders will be investigated whether they are important for discriminating FAV vs no-FAV and whether they are confounders (associated p<0.10 both to the group and the outcome).

Dichotomous outcome variables will be analysed using logistic regression, adjusted for identified confounders available at the time of study inclusion. Odds-ratios (OR) with 95% confidence intervals (CI) will be presented.

Time-to-event analyses will be performed using Cox proportional hazards models adjusting for identified confounders. Proportional hazards assumption will be checked by visually reviewing log(-log(survival)) vs log(time) graphs, and by adding interaction between treatment group and log(time) in the model, where significant interaction indicates non-proportionality. Other methods will be applied, e.g. Poisson regression for time varying data, allowing study of changes in treatment effects over follow-up time, in case non-proportionality of hazards occurs.

Time-to-event data will be described by using Kaplan-Meier technique.

The primary analyses for the FAV vs no-FAV group conducted on FAS_{ENR} population will be considered as confirmatory analyses and a total significance mass of 0.05 will be applied. The tests will be performed on the primary variable and the most important secondary variables using fix sequential testing procedure according to the following order:

1. Primary variable: Transplantation-free survival from fetal diagnosis to 2 years postnatal age, having a biventricular circulation without pulmonary hypertension at that time

2. Secondary variable: Transplantation-free survival from fetal diagnosis to 2 years of age

3. Secondary variable: Survival from fetal diagnosis to live birth at term (≥37 weeks)

4. Secondary variable: Proportion of included fetuses who have a biventricular circulation at neonatal hospital discharge

5. Secondary variable: Proportion of included fetuses who have a biventricular circulation at 2 years of postnatal age

This means that first test must be significant on 0.05 significance level in order to be able to further confirm the tests 2 to 5, and the second test must be significant on 0.05 level in order to be able to confirm tests number 3 to 5, etc.

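### Secondary survival analyses start the clock at fetal diagnosis but admit fetuses only at later inclusion, without delayed entry, so the hazard ratio leans toward whichever arm waited longer

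*SAP*

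**What the plan says.** SAP 3.4.2 lists "Transplantation-free survival from fetal diagnosis to 2 years of age (analysed as time to event" and "Survival from fetal diagnosis to live birth (analysed as time to event on" the enrolled full analysis set, with the enrolled per-protocol set as a further population. The analyses on the two at-birth sets are followed from birth and are complementary.

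SAP 4.1 gives the method: "Time-to-event analyses will be performed using Cox proportional hazards models adjusting for identified confounders", with Kaplan-Meier description. Neither section mentions delayed entry, left truncation, a landmark or a clock that starts at inclusion.

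Entry comes later than diagnosis. SAP 1.2 states: "Included are fetuses with a diagnosis of aortic stenosis who satisfy inclusion/exclusion criteria between 23+0 and 31+6 weeks of gestation". SAP 2.1.1 restricts the enrolled set to enrolled fetuses that met the criteria. SAP 3.1 records "Gestational age at primary diagnosis (weeks and days) (potential confounder") as a separate item from gestational age at the baseline echo.

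Three further provisions matter:
- SAP 1.4 fixes FAV status when the needle passes through the mother's abdominal wall.
- The Protocol's eCRF section takes the final pre-intervention examination as the FAV baseline echo, and allows an additional baseline echo after a late decision.
- SAP 4.1 names both gestational ages as known confounders but, if they prove highly correlated, keeps only the one with more influence.

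**The concern.** A fetus that dies between diagnosis and inclusion never enters the study. Every enrolled fetus therefore brings a stretch of time in which it could not have had an event, and a Cox model running from diagnosis counts that stretch as time at risk. This is left truncation that the plan does not handle.

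There are two consequences. First, the early part of a curve labelled as survival from diagnosis is too high in both arms, because it describes only fetuses that survived to inclusion. Second, if one arm waits longer, its hazard is diluted more and the hazard ratio moves in its favour with no treatment effect. The variables concerned are the second in the SAP 4.1 confirmatory sequence and, if it is analysed as time to event, the third.

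**Working it through.** **The plan's own figures.** The documents state no power, event count or hazard ratio for the time-to-event variables, so there is no planned figure to reproduce. The stated 91.8% power concerns the binary primary (60% v 30%, 100 v 50, Fisher's exact test). Exact enumeration gives 92.7%, close to it, and this has no bearing on the present point.

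**Inputs from the documents.** Clock from diagnosis (SAP 3.4.2); entry at 23+0 to 31+6 weeks (SAP 1.2); 100 FAV and 50 no-FAV (SAP 1.5); two-sided tests at 0.05 (SAP 4.1).

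**Assumptions, not in the documents.** No treatment effect; constant fetal hazard; diagnosis uniform over 20 to 28 weeks; fetal death risk of 5% or 15% per 14 weeks, which is −ln(0.95)/14 = 0.37% or −ln(0.85)/14 = 1.16% per week; death or transplantation after birth of 15% or 30% by 2 years; various diagnosis-to-inclusion delays.

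**Step 1, by hand.** Let T be the weeks in utero after inclusion (assumed 12 in both arms) and g the guaranteed event-free weeks before it. Events occur only during T, but the model divides by T + g. The apparent ratio is

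[T/(T + g_FAV)] / [T/(T + g_noFAV)] = (T + g_noFAV)/(T + g_FAV).

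- 2.5 v 1.3 weeks: 13.3/14.5 = 0.92
- 3.0 v 1.25 weeks: 13.25/15.0 = 0.88
- 4.7 v 1.25 weeks: 13.25/16.7 = 0.79
- equal gaps: 1.00
- 1.25 v 3.0 weeks: 15.0/13.25 = 1.13

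**Step 2, simulation of the Cox model from diagnosis, unadjusted (200,000 v 100,000 fetuses).** Ranges run over the four combinations of fetal and postnatal risk.

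| Realised mean gap, FAV v no-FAV (weeks) | HR, live birth | HR, 2-year transplantation-free survival |
|---|---|---|
| 1.25 v 1.25 | 0.99–1.02 | 0.99–1.01 |
| 2.1 v 1.25 | 0.93–0.95 | 0.97–0.98 |
| 3.0 v 1.25 | 0.85–0.87 | 0.93–0.97 |
| 4.7 v 1.25 | 0.71–0.73 | 0.88–0.95 |
| 1.25 v 3.0 | 1.13–1.18 | 1.01–1.07 |

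With delayed entry at inclusion, every scenario returns to 0.97–1.03. A separate null simulation at 2.5 v 1.3 weeks gave 0.91 for live birth, and 1.10 when no-FAV waited longer. The hand formula is milder at large gaps because it holds T equal; in the simulation, later inclusion also shortens the time left in utero.

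**Step 3, does the planned adjustment help?** Null hazard ratios for live birth, Cox from diagnosis:

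| Scenario | Age at diagnosis only | Age at inclusion only | Both ages | Delayed entry |
|---|---|---|---|---|
| Same diagnosis ages in both arms, gap 3.0 v 1.3 weeks, hazard 1.1% per week (unadjusted 0.85) | 0.86 | 0.90 | 1.00 | 0.99 |
| Mean diagnosis at 21 v 24 weeks, gap 3.5 v 1.2 weeks, hazard 1.2% per week | 0.92 | 0.80 | 1.00 | 1.00 |

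The Monte Carlo standard error in the first row is about 0.009. In the 2.5 v 1.3 scenario, one age alone left 0.91 to 0.94, and both gave 1.01. Conditioning on both ages fixes the gap itself; conditioning on one does not.

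**The case against.** **Adjustment is already planned.** This is the strongest reply, and part of it stands. It would be wrong to say that a gestational-age covariate cannot undo the bias, because keeping both ages does. In the second scenario of Step 3 the two ages correlated at only 0.54, so the rule for dropping one might not be triggered. But the SAP expects a high correlation, and if the rule applies, the bias remains.

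**The direction is not documented.** This stands. A reader might infer that the plan favours FAV. No section gives the delay by arm, and SAP 4.1 says only that age at diagnosis may vary between countries and centres, which is not the delay to inclusion. Some no-FAV 2 cases share the referral path, and the eCRF list places inclusion before counselling. Equal delays leave the hazard ratio unbiased, and a longer no-FAV delay reverses it.

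**Confirmatory error is protected by the sequence.** This largely stands. At 100 v 50 with the higher risks, unadjusted false findings for FAV on live birth were 5.5% (3.0 v 1.25 weeks) and 10.2% (4.7 v 1.25), against about 2.3% with delayed entry. A reader might take these for the trial's confirmatory error rate. They are not: they leave out the planned adjustment, and test 3 counts only if tests 1 and 2 succeed. In one unadjusted null simulation, tests 2 and 3 were jointly significant for FAV in 1.7% of runs, before any requirement on the primary.

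**Test 3 may not be time to event.** SAP 4.1 words it as live birth at 37 weeks or later, which could be a yes/no outcome; SAP 3.4.2 does not. The clock matters only under the time-to-event reading.

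**Conclusion.** The concern holds for the time-to-event secondary analyses on the enrolled sets. Time before inclusion is event-free by construction, and nothing in the SAP removes it from the risk sets.

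The bias follows the longer delay. FAV is the likelier beneficiary, because FAV status requires survival to the needle and its baseline echo is the final pre-intervention one, but that is an inference. Under the assumptions above, the null hazard ratio for live birth is about 0.85 to 0.91 at mean gaps of 2.5 to 3 v 1.3 weeks, and lower for wider differences. For 2-year transplantation-free survival the pull is small, about 0.93 to 0.97 at 3.0 v 1.25 weeks, because a few weeks are set against more than two years. Without earlier censoring, the Kaplan-Meier estimate at 2 years equals the simple proportion, so the distortion lies in the hazard ratio and the early curve.

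The issue is mainly bias in reported estimates rather than confirmatory type I error. A reader might extend it to the primary endpoint because its label also says from fetal diagnosis. SAP 3.4.1 makes that variable binary, so its model has no clock. The analyses followed from birth are also free of this defect.

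**What to change.** In SAP 3.4.2 and 4.1:

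1. Run the Cox and Kaplan-Meier analyses on the enrolled full analysis and per-protocol sets with delayed entry at inclusion, for example with gestational age as the time axis and the ENTRY option in SAS PHREG.
2. Define the entry date as the baseline echo. For FAV cases this is the final pre-intervention echo, including any additional baseline echo. Handle any remaining time to the needle with a landmark or a time-dependent exposure.
3. Label these secondary endpoints 'from inclusion'.
4. Report the diagnosis-to-inclusion delay by group.
5. Reconcile the wording of live birth in SAP 3.4.2 with test 3 in SAP 4.1, and state whether test 3 is time to event or binary.

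The cost is SAP wording and minor programming, with slightly lower reported early survival. The gestational ages needed are already collected.

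The primary analysis needs no change on this ground.
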